nitric oxide circuit is best represented by the compelling data in humans showing reduced blood pressure (12) and augmented exercise performance (13).

Since peak plasma concentrations of nitrate and nitrite occur within 1-2 hours and 3-4 hours (following ingestion) (14), respectively, there is a reasonable window of time to perform exercise. By harnessing the reasonable time (2-3 hours), during which, plasma nitrate and nitrite levels are at a maximum, beetroot juice consumption can be planned to coincide to the start of exercise to acutely elicit the following effects in postmenopausal women: 1) greater distance covered during a 6-minute walk; 2) increased endothelial-dependent vasodilation as determined by flow-mediated dilation and; 3) reduced endothelial microparticles (e.g. sVCAM-1, sICAM-1, sE-selectin). Potential findings could inform a larger clinical trial to determine if pre-exercise beetroot supplementation is an efficacious strategy to promote health related effects of exercise training including improved gait/mobility and reduced CVD risk. *To test our hypotheses, we propose a 2-arm randomized controlled pilot to examine the following aims:*

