### **2.2 Secondary Objective**

**Aim 2a.** Determine preliminary effects sizes for pre-exercise beetroot juice consumption + exercise training (BR+EX) compared + exercise training only (EX) on distance (feet) covered during a 6-minute walk test. Performance during the 6-minute walk has been shown to accurately estimate peak oxygen uptake (i.e., aerobic fitness) and functional mobility. Consistent with others showing performance benefits of pre-exercise beetroot juice consumption and acute exercise, we anticipate a small to medium effects size in a beneficial direction (i.e., greater positive change) for BR+EX compared to EX.

**Aim 2b.** Determine preliminary effect sizes for BR+EX compared to EX on improvement of endothelial-dependent vasodilation as evidenced by percent increase in flow-mediated dilation. Based on our working premise that beetroot juice may offset the burdens of endothelial dysfunction/activation by increasing nitric oxide bioavailability, coupled with the effects of exercise training, we anticipate a small to medium effect size in a beneficial direction for BR+EX compared to EX.

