#### **3.2 Secondary Outcome Measures**

**2a.** The distance (feet) covered during a 6-minute walk test at baseline prior to the intervention and following BR+EX is the main secondary outcome of interest. To confirm the relationship of the functional 6-minute walk test to aerobic fitness, measures of oxygen consumption (ml/kg/min or L/min), heart rate (bpm), and blood pressure (mm Hg) will be taken during constant speed walking at a typical walking pace prior to the 6-minute walk test. Additionally, functional mobility will be assessed by analyzing triaxial movement patterns from an accelerometer worn on the non-dominant hip during the 6-minute walk test.

The BR+EX intervention will be considered successful in the event that there is a statistically significant increase in 6-minute walk distance (feet) along with a decrease in oxygen consumption (ml/kg/min or L/min), decrease in exercising heart rate (bpm), improvement in heart rate recovery following exercise (post exercise heart rate – heart rate 1 min, 2 min after exercise (bpm)), decrease in exercising blood pressure (mm Hg), decrease in post-exercise blood pressure (mm Hg), and/or improvement in gait function (i.e. preferred walking speed, center of mass characteristics) from baseline to post-intervention above any improvement seen in EX.

**2b.** Percent changes in brachial artery diameter (%), cutaneous vascular conductance (%), and pulse wave velocity (m/s) at baseline prior to the intervention and following BR+EX are secondary outcomes of interest, representing changes in endothelial dependent vasodilation. A non-invasive technique of flow mediated dilation of the brachial artery using ultrasound imaging will be used to assess the percent change in vessel diameter following occlusion. A local heating protocol using non-invasive Laser Doppler flowmetry in conjunction with blood pressure measurements will be used to obtain measures of red blood cell (RBC) flux and mean arterial pressure (MAP) to calculate cutaneous vascular conductance (RBC flux/ MAP). The velocity of the pulse wave traveling from the carotid to femoral artery will be assessed non-invasively using tonometry.

A statistically significant increase in the percent change in brachial artery diameter (%), cutaneous vascular conductance (%), and/or a decrease in pulse wave velocity (m/s) in BR+EX above any improvement observed in EX from baseline to post-intervention will be considered a successful outcome.

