## 5.0 Study Design

To fulfill the purposes outlined above, a 2-arm randomized controlled study design will be employed. After completing initial screening procedures (**screening visit**), subjects will return

to the School of Public Health at Indiana University Bloomington to have baseline measures of weight, body composition, bone density, heart rate, cutaneous vascular conductance, blood pressure, assessed prior to and 3-hours following ingestion of beetroot juice (**Visit 1**). During this visit, two questionnaires will be administered to obtain information related to the health history, physical activity habits, mood state, and cognitive abilities of the subjects. Following a minimum 7-day washout period, to mitigate the risk of any carry-over effect from the acute dose of beetroot juice administered during the initial visit, subjects will have their blood drawn at the Indiana University Student Health Center followed by measures of weight, body composition, and pulse wave velocity performed at the School of Public Health at Indiana University Bloomington (**Visit 2**). During this visit they will also perform two 6-minute walking tests, and muscle function test. After baseline assessments **Visits 1-2**, participants will be randomly assigned to one of two study arms. All study arms will complete an 8-week exercise training protocol. The first arm will serve as a control group and will require participants to only complete the 8-week exercise training protocol (EX). The second arm will complete exercise training with ingestion of a beetroot (BR+EX). Exercise training will occur no more than 6 weeks following baseline Visit 2 to minimize the effects of potential changes in physical conditioning/deconditioning on baseline measures. Subjects will be asked to repeat baseline Visit 2 before initiating exercise training in the event >6 weeks lapses from the completion of the final baseline assessment visit.

The same procedures as performed in **Visits 1-2** will be repeated following the treatment intervention for **Visits 3-4** in reverse order. The procedures outlined for **Visit 2** will be performed during **Visit 3**, and procedures for **Visit 1** for **Visit 4**.

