**Pulse Wave Velocity (PWV)**- Measurements of PWV (m/s) will be obtained from standard blood pressure and tonometry assessment using the ATCOR SphygmoCor device. This device is a non-invasive way to perform central blood pressure waveform assessment. During **Visits 2 and 2**, subjects will be asked to lie still in a supine position on a padded table surface for a duration of 10 minutes. A leg blood pressure cuff will be placed on the upper thigh. A technician will apply carotid tonometry simultaneously to inflating the blood pressure cuff to obtain blood pressure waveforms at the carotid and femoral artery sites. SphygmoCor software uses physical distance measurements between the sites to calculate velocity.

**Laser Doppler Blood Flow Heating Protocol**- Laser Doppler (Blood FlowMeter, Ad Instruments) will be used to assess cutaneous vascular conductance in response to a localized heating stimulus. Two small skin surface probes will be applied to the non-dominant forearm of the subject during **Visits 1 and 4**. Resting measurements will be obtained for 5 minutes followed by a measure of resting blood pressure. Localized skin heating will be accomplished with local heating units that will surround the skin surface probes of the laser Doppler. Both probes will be heated to a set temperature of 39°C (102°F) for 25 minutes. . The temperature of the probes will then be increased until a maximum temperature of 44°C (111°F) and held for 15 minutes . Blood pressure measurements will be obtained from the dominant arm every 10 minutes during the 40-minute heating protocol. From measures of blood pressure and the laser Doppler blood flow, cutaneous vascular conductance will be calculated as a ratio of skin blood flow to mean arterial pressure. Cutaneous vascular conductance will be expressed as a percentage of maximal conductance measured at the end of the heating protocol.

**Blood Pressure**- Blood pressure readings (mm Hg) of systolic and diastolic blood pressure will be taken using an automated sphygmomanometer on the dominant upper arm. During **Visits 1 and 4**, measurements will be taken during seated rest, every 10 minutes during the localized heating protocol, and every hour for 3-hours following ingestion of beetroot juice. During **Visits 2 and 3**, measurements will be taken during standing rest prior to the submaximal walking exercise, at minutes 3 and 5 during submaximal walking, and after 3 minutes of recovery following submaximal walking.

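### Aim 2b is defined only by flow-mediated dilation, which has no procedure and no visit; align the aim, outcomes and calendar before any outcome data are examined

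*Combined protocol and SAP*

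**What the plan says.** FMD is named in three places.

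- Section 1.0 gives it as one of three expected effects: "increased endothelial-dependent vasodilation as determined by flow-mediated dilation". The other two are 6-minute walk distance and endothelial microparticles.
- Section 2.2, Aim 2b, seeks an effect size for "improvement of endothelial-dependent vasodilation as evidenced by percent increase in flow-mediated dilation". No other measure is named in the aim.
- Section 3.2 lists brachial artery diameter, CVC and PWV together; these "are secondary outcomes of interest, representing changes in endothelial dependent vasodilation". It adds that "flow mediated dilation of the brachial artery using ultrasound imaging will be used to assess the percent change in vessel diameter following occlusion", without giving a visit.

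The 2b success rule in Section 3.2 accepts a significant benefit over EX in "percent change in brachial artery diameter (%), cutaneous vascular conductance (%), and/or a decrease in pulse wave velocity (m/s").

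Section 5.0 sets out the visits. Visit 1 takes "baseline measures of weight, body composition, bone density, heart rate, cutaneous vascular conductance, blood pressure, assessed prior to and 3-hours following ingestion of beetroot juice". The list for Visit 2 is "weight, body composition, and pulse wave velocity performed at the School of Public Health", besides the blood draw, walking tests and muscle function test. Visits 3 and 4 repeat these in reverse order. FMD is in neither list.

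Section 12.0 says that the pilot is meant to supply effect sizes for a larger study. It plans an unpaired t-test and Cohen's d for Aim 2b.

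**The concern.** An aim needs a measurement, and this one has a name and a technique but no place in the schedule. A team that follows Sections 5, 7 and 8 exactly will finish the study with no FMD data, and the effect size that Section 12.0 plans for Aim 2b cannot be calculated.

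The success rule makes the gap easy to overlook. Because it is an and/or rule, 2b can be declared successful on CVC or PWV although the aim mentions neither. If the mismatch is resolved only after results are known, the effect size reported for Aim 2b could be chosen by its value.

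If CVC is to carry the aim, its own definition also has gaps. It is recorded before and after juice that both arms drink, with neither recording designated for the between-arm comparison, and the length of heating is stated in two ways.

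**Working it through.** The plan states no sample size or power figure for Aim 2b, so there is none to reproduce. The check sets the places side by side.

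| Place | FMD | CVC | PWV |
|---|---|---|---|
| Section 1.0, expected effects | yes | no | no |
| Section 2.2, Aim 2b | yes | no | no |
| Section 3.2, 2b outcomes | yes | yes | yes |
| Section 5.0, design | no | Visit 1 | Visit 2 |
| Section 7.0, procedures (17 headings) | no | Visits 1 and 4 | yes, but Visit 2 is printed twice |
| Section 8.0, visit narratives | no | Visit 1, before and after juice | Visit 2 |
| Section 8.0, table (29 rows) | no | heating-protocol row | PWV row |

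**Count over the last four rows,** which describe or schedule measurements: FMD 0 of 4, CVC 4 of 4, PWV 4 of 4. Of the three outcomes listed for 2b, two are scheduled. Of the one measure named in Aim 2b, none is. The attachments listed in Section 17.0 include no FMD procedure.

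**CVC recordings.** Section 8.0 runs the heating protocol before the juice and repeats it about 3 hours after, at Visit 1 and again at the matching follow-up visit: 2 recordings × 2 visits = 4 per participant. Both arms drink the juice at these visits. The pre-juice pair compares the arms without an acute dose on the day; the post-juice pair adds the acute response. No section says which pair is the 2b outcome.

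**Heating duration.** Section 7.0 says "Both probes will be heated to a set temperature of 39°C (102°F) for 25 minutes", then holds 44°C for 15 minutes: 25 + 15 = 40 minutes, which agrees with its own total. The Visit 1 narrative in Section 8.0 gives 30 minutes and no split by stage. CVC is scaled to the maximum reached when heating ends, so time at 44°C matters. Assuming a 30-minute protocol keeps one of the two stages intact:

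- 39°C stage kept at 25 minutes: 30 − 25 = 5 minutes at 44°C, and (15 − 5)/15 = 67% shorter.
- 44°C stage kept at 15 minutes: 0% shorter.

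The range is therefore from no change to two thirds less time at 44°C.

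**PWV visits.** The PWV procedure prints Visit 2 twice. Section 5.0 moves Visit 2 procedures to Visit 3 at follow-up, and the table marks PWV at the first follow-up visit, so Visits 2 and 3 are implied.

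**The case against.** Section 3.2 names all three 2b outcomes in advance and Section 12.0 fixes the analysis, so selection by result is a risk and not something the plan invites. This is also a feasibility pilot: the primary outcomes are recruitment, retention, adherence, perceived difficulty and adverse events, and 6-minute walk distance is the main secondary outcome. Both statements are correct and limit the weight of the point. Neither supplies an FMD measurement.

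A reader might infer that FMD is a singular omission which loose drafting cannot explain. The documents do not support that. The walking-speed and centre-of-mass terms in the 2a success rule of Section 3.2 also have no named procedure, visit or calendar row. General incompleteness may well be the cause; the aim is unanswerable either way.

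A reader might also take FMD to be the trial's vascular hypothesis as a whole. Section 1.0 makes it one of three expected effects, and another of those, reduced endothelial microparticles, is also vascular.

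On heating, Section 7.0 is the detailed account and is internally consistent, while Section 8.0 is a summary. Nothing shows that some visits used 30 minutes and others 40, and one duration used throughout would apply equally to both arms. What stands is that the two statements conflict.

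Finally, dropping FMD is a scientific choice as well as a change of wording. That objection stands in full, so the two routes below are offered without a preference.

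**Conclusion.** The point holds. As written, the plan schedules no data for the only measure Aim 2b names (0 of 4 places, against 4 of 4 for CVC and for PWV), so the planned Aim 2b effect size cannot be produced, while 2b success remains open through the two other outcomes. It should be fixed. It does not touch the primary feasibility aim.

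The conclusion rests on the text of Sections 1 to 3, 5, 7, 8, 12 and 17. The study schema figure is not visible in the text reviewed, so a mention of FMD there cannot be excluded, but it would not fill the gap in Section 7 or the calendar table. A reader might infer that FMD was never measured, or that heating times varied between visits; the documents show neither. The two-thirds figure is the upper end of a range that starts at zero and depends on the stated assumption about stages.

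**What to change.** Before any outcome data are examined, make Sections 1.0, 2.2, 3.2, 7.0 and 8.0 agree by one of two routes.

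1. **Restate Aim 2b and its success sentence on the outcomes already listed and scheduled.** Use CVC as the endothelial measure and label PWV as arterial stiffness, in line with Section 12.0, which lists endothelial function and arterial stiffness separately. Remove FMD from Sections 1.0, 2.2 and 3.2. This adds no visit, test or participant. The cost is scientific: the trial makes no FMD claim, and CVC is the only measure of endothelial vasodilation left.
2. **Keep FMD and schedule it.** Write a Section 7.0 procedure and name its baseline and follow-up visits. If it is placed at Visits 1 and 4, state its timing relative to the juice. At one scan per visit this is 24 × 2 = 48 scans for the 24 randomized in Section 3.1, or 36 × 2 = 72 for the 36 in Section 6.0, before dropout. If FMD were taken both before and after the juice, the numbers double to 96 and 144. Participants already past baseline cannot supply a baseline scan.

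Under either route:

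- state which CVC recording, before or 3 hours after the juice, is the between-arm outcome, and report the other descriptively;
- reconcile the 40-minute heating protocol in Section 7.0 with the 30-minute one in Section 8.0;
- correct the visit label in the PWV procedure so that it agrees with Section 5.0 and the calendar table.

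These three are text edits and add no procedure.

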### 3.3 Tertiary/Exploratory/Correlative Outcome Measures

Tertiary outcome measures of interest include plasma concentrations of sICAM-1, s-VCAM-1, sNCAM, MPO, IFN $\gamma$ , IL-1 $\beta$ , BDNF, TNF- $\alpha$ , and IL-10 obtained from a venous blood sample taken at baseline and post-intervention.

Statistically significant decreases in endothelial microparticle concentrations from baseline to post-intervention in BR+EX that are above any decrease observed in EX will be considered a successful outcome.

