### **2.3 Tertiary/Exploratory/Correlative Objectives**

**Aim 3.** Determine preliminary effect size for BR+EX compared to EX on reducing soluble endothelial microparticles including, sICAM-1, sVCAM-1, sNCAM, MPO, IFN $\gamma$ , IL-1 $\beta$ , BDNF, TNF- $\alpha$ , and IL-10. Given the link between nitric oxide and regulation of NF- $\kappa$ B, it is reasonable that BR+EX may have synergistic properties that could contribute to

favorable effects on the vascular endothelium. As such, we anticipate a small to medium effect size in a beneficial direction for BR+EX compared to EX.

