**Questionnaires**- A questionnaire will be given to participants in two parts (Part A and Part B) during **Visits 1 and 4**. The first part of the questionnaire consists of the Addenbrooke's Exam-III (ACE-III), which will be verbally administered by a trained member of our research team. This exam is designed to assess five cognitive domains including attention, memory, verbal fluency, language, and visuospatial abilities. Current mood states will be assessed using the Profile of Mood States (POMS) instrument. These questionnaires are also designed to obtain demographic, health, and physical activity habit information about our subjects.

**Venous Blood Draw-** A venous blood sample will be taken by trained personnel at the Indiana University Bloomington Student Health Center during **Visits 2 and 3**. Two 7mL, and one 4mL vials of blood will be taken at each timepoint for a total of 18mL x 2 visits = 36mL. The two 7mL vials of EDTA plasma samples will be centrifuged 1 x 10 minutes at 2500 x g at room temperature. Samples will then be aliquoted and stored at -80 degrees Celsius. Upon thawing, samples will be prepped wherein quantification of endothelial microparticles (sICAM-1, s-VCAM-1, sNCAM, MPO, IFNg, IL-1 $\beta$ , BDNF, TNF- $\alpha$ , and IL-10) will be performed. Flow cytometry will be used to obtain a complete blood count (CBC) using the 4mL vial of EDTA plasma sample.

**Nitric Oxide Breath Analysis-** The fraction of expired nitric oxide in exhaled breath will be assessed using a handheld digital breath analyzer (NIOX VERO). Subjects will be asked to exhale once into the analyzer prior to ingestion of beetroot juice and again 3-hours after ingestion to confirm a change in nitric oxide levels at **Visits 1 and 4**. During **weeks 3 and 6 of the supervised exercise training intervention**, random drop-ins will be conducted by a member of our research team to assess fractional exhaled nitric oxide levels to assess compliance with the beetroot supplementation by asking subjects to breathe once into the breath analyzer.

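### Section 3.3 judges Aim 3 on endothelial microparticle concentrations, but the plan measures nine soluble plasma proteins and describes no microparticle measurement

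*Combined protocol and SAP*

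**What the plan says.** The term microparticle appears in four places in the combined protocol and SAP.

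- **Section 1.0 (Background & Rationale)** lists, among the acute effects expected from juice before exercise, "reduced endothelial microparticles (e.g. sVCAM-1, sICAM-1, sE-selectin".
- **Section 2.3 (Aim 3)** seeks a preliminary effect size for "reducing soluble endothelial microparticles including, sICAM-1, sVCAM-1, sNCAM, MPO" and five further analytes.
- **Section 3.3** first defines the outcome: "Tertiary outcome measures of interest include plasma concentrations of sICAM-1, s-VCAM-1, sNCAM, MPO" and the same five others. It then sets the success rule on "Statistically significant decreases in endothelial microparticle concentrations from baseline to post-intervention in BR+EX", beyond any decrease in the exercise-only arm.
- **Section 7.0 (Venous Blood Draw)** describes the laboratory work as "quantification of endothelial microparticles (sICAM-1, s-VCAM-1, sNCAM, MPO" and the same five others.

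Section 7.0 also gives the sample handling: "The two 7mL vials of EDTA plasma samples will be centrifuged 1 x 10 minutes at 2500 x g at room temperature", followed by aliquoting and freezing. Its only mention of flow cytometry concerns a separate tube: "Flow cytometry will be used to obtain a complete blood count (CBC) using the 4mL vial of EDTA plasma sample".

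Section 12.0 assigns Aim 3 an unpaired t-test and Cohen's d. It refers to inflammation and its markers, and does not use the word microparticle.

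**The concern.** Within Section 3.3 the quantity measured and the quantity judged have different names. In ordinary usage a microparticle is a small membrane vesicle, and an endothelial one has been shed by an endothelial cell. A soluble protein in plasma is a different thing. If the success rule is applied as worded, the trial's report could claim an effect on endothelial microparticles when the data concern dissolved proteins.

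The pilot exists to supply effect sizes for a larger study. An effect size filed under the wrong construct could be carried into that study's choice of outcome.

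The single label also hides a second gap. Because the rule names no analyte, it gives one direction for the whole panel. A fall in IL-10 or BDNF would count towards success on the same terms as a fall in TNF-alpha, and the plan does not say why a fall in each of the nine is the favourable result.

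**Working it through.** The plan gives no figure to reproduce here, so the check sets the sections side by side.

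**Step 1. What is on the panel.** Sections 2.3, 3.3 and 7.0 give the same list. Grouped by type:

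| Type | Analytes | Number |
|---|---|---|
| Adhesion molecules | sICAM-1, sVCAM-1, sNCAM | 3 |
| Enzyme | MPO | 1 |
| Cytokines | IFN-gamma, IL-1beta, TNF-alpha, IL-10 | 4 |
| Neurotrophic factor | BDNF | 1 |

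The total is 3 + 1 + 4 + 1 = 9. The three lists agree exactly. All nine are proteins, and Section 3.3 reports them as plasma concentrations.

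**Step 2. Whether any microparticle measurement is described.** Section 7.0 gives one spin, aliquoting, freezing, thawing and quantification of the nine analytes. It has no step to isolate, label or count particles. Flow cytometry is assigned only to the blood count, from the 4 mL tube. The Section 8.0 calendar lists only a venous blood draw. The number of microparticle measurements described is therefore zero. The assay platform for the nine analytes is not named, so this rests on what the plan describes.

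**Step 3. What the success rule tests.** The first sentence of Section 3.3 names the nine proteins. The second judges success on microparticle concentrations. The two can be joined only by treating the proteins as the microparticles, which is what "quantification of endothelial microparticles (sICAM-1, s-VCAM-1, sNCAM, MPO, IFNg" and the rest of that parenthesis in Section 7.0 do. With that substitution, a significant fall in MPO, TNF-alpha or BDNF falls under the microparticle label.

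**Step 4. Direction.** Section 2.3 speaks of reducing the whole list, and Section 3.3 speaks of decreases. Neither gives a direction by analyte. Section 2.3 also expects a beneficial direction, but the plan never says that lower is beneficial for each of the nine. For IL-10, usually regarded as anti-inflammatory, and BDNF, a neurotrophic factor, this is not self-evident. Those descriptions are general knowledge and are not stated in the plan.

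**Step 5. Background against panel.** Section 1.0 names sVCAM-1, sICAM-1 and sE-selectin. Removing the markers that are on the panel leaves sE-selectin, which appears nowhere else in the document.

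**The case against.** The strongest reply is that no careful reader would be misled. Section 7.0 equates the label with a closed list of nine analytes, Section 3.3 defines the outcome as their plasma concentrations one sentence before the rule, and Section 2.3 qualifies the term as soluble. Section 12.0 does not use the term. This is fair as to what will be assayed, and it is why severity is low. It does not rescue the success rule, which is the sentence that says what Aim 3 may conclude and which still names a construct the plan does not describe measuring.

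Several stronger readings are tempting, and the documents do not support them.

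- *A pre-specified endpoint, sE-selectin, was dropped.* In Section 1.0 it is one of several examples, in a sentence about acute effects. It is not in Aim 3 or the outcome list. Its absence is a mismatch between background and panel.
- *Most of the panel lies outside the hypothesis.* Section 2.3, the formal aim, names all nine analytes and gives a rationale through nitric oxide and NF-kappaB.
- *The endothelial question is diluted by the other analytes.* No composite is defined, and Section 12.0 states no multiplicity adjustment. The additional analytes leave the sICAM-1 and sVCAM-1 estimates and tests unchanged.
- *A fall in any one analyte is enough for success.* Section 3.3 does not say so. It leaves open how many analytes must fall. A familywise error figure would need that number, an alpha and the correlation among analytes. The plan gives none of these, so no such figure is offered.
- *Only sICAM-1 and sVCAM-1 should count as endothelial outcomes.* That is a debatable preference about ranking outcomes. Nothing in the documents establishes it, and all nine are already tertiary.

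**Conclusion.** The concern holds as a fault in the success rule and in the name of the construct. Section 3.3 judges Aim 3 on endothelial microparticles, whereas the plan measures nine soluble proteins and describes no microparticle measurement. The rule also applies one undifferentiated direction to all nine. The sE-selectin mismatch in Section 1.0 is a minor inconsistency alongside it.

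Severity is low. Aim 3 is tertiary, the study is a pilot seeking preliminary effect sizes, and nothing in the primary feasibility outcome, randomisation, blood sampling or t-tests depends on the label. What changes is the conclusion that Aim 3 may state.

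The verdict rests on two assumptions: that microparticle carries its ordinary meaning of a membrane vesicle, and that no particle assay is planned beyond what Section 7.0 describes. A reader might infer that the Aim 3 data will be unusable. They will not be: the nine concentrations can be reported under their own names.

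**What to change.** Make three wording changes, preferably before Aim 3 is analysed.

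1. In Sections 1.0, 2.3, 3.3 and 7.0, replace the microparticle term with *soluble markers of endothelial activation and inflammation*.
2. In Section 3.3, restate the success rule by analyte name, with the investigators' expected direction of change for each of the nine, including IL-10 and BDNF. Limit any conclusion to the analytes measured.
3. In Section 1.0, remove sE-selectin from the examples, since it is not on the panel.

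The cost is an amendment to wording. No new sample, assay, visit or analysis method is needed, and the tertiary status of all nine analytes stays as it is.
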